The participants and their parents were recruited from June 1, 2013, through December 31, 2017. All outpatients aged 13–18 years meeting the diagnostic criteria for Anorexia nervosa (AN) and admitted to the Family based treatment (FBT) at the Eating Disorder Unit of Helsinki University Hospital were invited to participate in the study. During the study period, 428 adolescent patients started outpatient treatment at the Eating Disorder Unit. Of those, 52 female patients diagnosed with AN, with a mean age of 14.50 ($SD = 1.31$) years, were admitted to FBT, and all of them participated in the study. The mean BMI at the beginning of treatment was 16.42 ($SD = 1.48$). On average, the participants had suffered from eating disorder symptoms for 13.29 ($SD = 8.15$) months before FBT started.

Intervention

On the patient's first visit to the unit, the attending psychiatrist usually makes a clinical decision of whether FBT is suitable for the patient. The decision is based on an assessment of the patient's medical and mental state, compliance to treatment, and family functioning. At the unit, FBT is carried out by a family therapist who has received FBT training. The duration of FBT is commonly 6–12 months, in most cases comprising 10–20 sessions. At the beginning of treatment, there are weekly sessions; later in treatment, the sessions are less frequent. The patient and their family meet their psychiatrist every four to six weeks, and the family therapist also takes part in these meetings. The treatment is implemented in accordance with the FBT treatment manual, but in a few cases, the FBT protocol was modified to have an increased number of sessions and longer duration due to the patient's clinical condition.

Treatment characteristics

The number of FBT treatment sessions ranged from 5 to 40 (*Mean* = 15.3, *SD* = 7.34). In 11 cases (21.2%), the treatment demanded more than 20 sessions. The treatment lasted up to 23 months, with an average duration of 10.25 (*SD* = 5.0) months. In all cases but one, FBT was finished in accordance with the clinical situation and treatment plan, and only one family dropped out of treatment. This withdrawal happened after session 10 of FBT when the family decided to continue the treatment at a private clinic. As the participant had participated in half of the planned FBT sessions before dropping out and had achieved change in weight and eating disorder symptoms, we did not exclude her from the study.

Assessments

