Pre-treatment information about the patients' growth and health before eating disorder onset, as well as diagnostic evaluations of comorbid psychiatric disorders, was gathered from their medical records. Assessment at baseline and at the end of treatment (EOT) included weight, height, eating

disorder symptoms, and psychopathology. According to FBT protocol, weight was assessed before every treatment session. The participants were weighed in their underwear on a balance beam scale that was regularly re-calibrated. According to the World Health Organization's (WHO) definitions, normal body weight was defined as a BMI ≥ 18.5 .

The attending psychiatrists' assessments of eating disorder symptoms and psychopathology at baseline and at EOT were used. The participants' caregivers, as well as their therapist, had a chance to express their opinion regarding whether the patient benefited from FBT or not.

Statistics

The statistical analyses were performed using IBM SPSS Statistics 25. First, the data was analyzed for descriptive parameters and incidence rates of all the variables. According to skewness and kurtosis, the data was mostly normally distributed. To assess treatment outcomes, the change in BMI was tested using a two-way analysis of variance for repeated measures, and the McNemar chi-square test was used to analyze the change in the incidence rates of symptoms. Further, for comparing groups of patients at EOT, Student's *t*-test and chi-square tests were used. All analyses were two-tailed. The alpha level was set at $p \leq 0.05$. We also calculated Cohen's *d* to estimate the effect sizes of statistically significant differences in the *t*-test, interpreting an effect size of 0.2 to 0.5 as small, 0.5 to 0.8 as medium, and over 0.8 as large. For the chi-square test, the phi (ϕ) coefficient was a measure for the effect size. A value of 0.1 was considered a small effect, 0.3 a medium effect, and 0.5 a large effect.

Results

At EOT, a majority (73.1%) had achieved a normal body weight [body mass index (BMI) ≥ 18.5]. Participants with a BMI ≥ 18.5 at EOT had a significantly higher pre-treatment BMI than those with BMI < 18.5 at EOT. Participants with a BMI ≥ 18.5 at EOT showed significantly higher total weight gain during the treatment period, a significantly higher rate of regular menstrual period at EOT,

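### Does the comparison of total weight gain between end-of-treatment BMI groups need to account for how long each patient was treated?

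*Combined protocol and SAP*

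**What the plan says.** The Results section divides the 52 patients by BMI at EOT, with 73.1% at or above 18.5, and reports that this group "showed significantly higher total weight gain during the treatment period".

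The Statistics section gives two relevant methods. For the sample as a whole, "the change in BMI was tested using a two-way analysis of variance for repeated measures"; the second factor is not named. Student's t-test and chi-square tests were used "for comparing groups of patients at EOT". Neither is described as using elapsed time, number of sessions or treatment length.

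Treatment characteristics describes when EOT occurred. "The treatment lasted up to 23 months, with an average duration of 10.25" months (SD 5.0). "The number of FBT treatment sessions ranged from 5 to 40", with mean 15.3 and SD 7.34, and 11 patients had more than 20. On the reason for stopping: "In all cases but one, FBT was finished in accordance with the clinical situation and treatment plan". The exception was a family that withdrew: "This withdrawal happened after session 10 of FBT".

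Under Assessments, weight was taken before each session, while height is listed only at baseline and EOT. Treatment length is given for the whole sample and not by EOT BMI group.

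**The concern.** Total gain is average rate multiplied by time. If patients who reached BMI 18.5 were also treated longer, a higher total gain could arise with no difference in how fast anyone gained. If they were treated for the same time or less, the same result would point to faster gain. These are different messages about family-based treatment, and an unadjusted t-test on total gain does not distinguish them.

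The variation in length is too large to dismiss, and length was not set by design: some treatments were extended because of how the patient was doing. With weights taken at every session, a time-based analysis also looks within reach. On a first reading, then, an available analysis seems to have been passed over for one that mixes rate with exposure.

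**Working it through.** **1. Counts.** From N = 52: 38/52 = 73.1%, which reproduces the reported share, leaving 14 below 18.5. 11/52 = 21.2% had more than 20 sessions, leaving 41 with 20 or fewer.

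**2. Spread of treatment length.** 5.0/10.25 = 0.49. One SD either side of the mean is 5.25 to 15.25 months, and 15.25/5.25 = 2.9. Time available to gain weight varied widely.

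**3. Could length alone give the reported result?** Suppose every patient gains at the same monthly rate. Then the standardised difference in gain equals the standardised difference in length, Δ/5.0. For 38 against 14 patients at two-sided 0.05:

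| Assumed difference in mean length (months) | Chance that total gain differs significantly |
|---|---|
| 1 | 9% |
| 2 | 25% |
| 3 | 48% |
| 4 | 73% |
| 5 | 89% |

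A simulation goes one step further. Its assumptions are a common rate of about 0.35 BMI units per month (set so that 73.1% reach 18.5), gamma durations cut to 1–23 months (realised mean about 9.9, SD about 4.5), and normal baseline BMI (16.42, SD 1.48) independent of duration. The upper group is then treated for about 11.2 against 6.4 months and gains about 3.9 against 2.2 BMI units. The t-test on gain is significant in about 99% of samples. Length alone can therefore produce the result. This shows what is possible, not what happened.

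**4. Could the grouping alone give it?** A patient is in the upper group exactly when BMI gain ≥ 18.5 − baseline BMI. At the mean baseline that is 18.5 − 16.42 = 2.08 units. Gain helps to define the group, so a higher gain there is partly built in, even if everyone is treated for the same time. Adjusting for length would not remove this.

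**5. What would treatment length by group settle?** Assume the overall SDs hold in both groups. √(1/38 + 1/14) = 0.3126 and t(0.975, 50 df) = 2.009.

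- Months: 2.009 × 5.0 × 0.3126 = 3.1
- Sessions: 2.009 × 7.34 × 0.3126 = 4.6

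By the table in step 3, a 3-month difference would by itself make total gain significant about half the time. A non-significant difference in length would not exclude length as the explanation.

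**6. What would a fixed-time model settle?** With the stated mean and SD, the expected number still in treatment is:

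| Assumed shape | Month 6 | Month 12 |
|---|---|---|
| Normal | 41.7 | 18.9 |
| Gamma | 41.6 | 16.2 |
| Lognormal | 42.8 | 14.7 |

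If the groups stayed in proportion, the 15–19 patients at month 12 would include about 4 to 5 below 18.5 (15 × 14/52 = 4.0; 19 × 14/52 = 5.1). The model would need about 52 × 15.3 = 796 session weights. The document says they were measured, not that they were extracted. Slopes compared between groups defined by EOT BMI are still conditioned on their own end point.

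**7. A split at 20 sessions.** If k of the 11 patients with more than 20 sessions reached 18.5, the rate among the other 41 is (38 − k)/41, from 27/41 = 65.9% to 38/41 = 92.7%. This only bounds an unreported cell. It says nothing about the weight-gain comparison, and session count is a poor clock because, in the Intervention section, "At the beginning of treatment, there are weekly sessions; later in treatment, the sessions are less frequent".

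**The case for a change.** The strongest case for a change is that time is a component of the outcome, not a remote confounder, and that a common-rate model reproduces the reported pattern almost every time. In that simulation, higher gain and higher baseline BMI in the upper group, both of which the Results report, were significant together in about 98% of samples. The title speaks of effects of treatment, so a reader may take the comparison as a statement about how well treatment works. Treatment length and session counts by group could be tabulated from data already held.

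Most of these facts stand: EOT timing is specific to each patient, no stated test allows for it, and length by group is not given. The inference to a fault does not. Longer treatment in the upper group follows largely from the simulation's own assumptions of one rate and of length unrelated to baseline BMI. The Intervention section says that some treatments were prolonged because of the patient's state, which could equally make the lower group the longer-treated one. Length is also partly a consequence of response, so adjusting for it poses a different question and does not simply remove a nuisance.

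The silence about length by group may itself be brevity. The Statistics section says descriptives were run for all variables, and the Results are a short summary naming mainly significant differences. The document does not settle whether the comparison was made.

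One side point falls away. The Intervention section says the protocol was modified in a small number of cases, while 11 patients had more than 20 sessions. These do not conflict, because the text does not equate a modified protocol with exceeding 20 sessions, and 41 of 52 staying within 20 fits its description of the usual course.

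**Conclusion.** No change to the plan is needed; this is a fair trade-off. Analysis at a clinically determined end of treatment answers a legitimate question for a single-arm description of routine care: where patients stood when treatment finished, and how much they had gained by then. The quantity is named correctly, the variation in length is disclosed, and no statement about speed of gain is made. Following the stated methods produces no wrong number and no wrong conclusion.

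The limit is one of interpretation. The higher total gain is a descriptive, cumulative difference between groups partly defined by that gain, and it should not be read as faster gain. A table of treatment length and sessions by group would be a useful courtesy in a full report. With half-widths of about 3.1 months and 4.6 sessions it probably could not separate the two explanations.

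This rests on the overall SDs holding within groups, on the assumed shapes for treatment length, and on the document making no claim about rate. A report that claimed faster gain would need a time-based analysis to support it.

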significantly lower rates of dietary restrictions, and less cognitive or behavioral symptoms of the eating disorder overall, compared to participants who did not achieve a normal body weight. In 22 cases (42.3%), there was no need for further treatment at the end of FBT. Participants who needed further treatment after FBT, compared to those who did not, showed significantly higher rates of psychiatric comorbidity, history of mental health treatment, and need for psychopharmacological treatment.

Competing interests

The authors declare no conflict of interest

List of abbreviations

AN = Anorexia nervosa

BMI = body mass index

EOT = end of treatment

FBT = Family-based treatment

WHO = World Health Organization

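### The weight-group symptom comparison describes status at the end of treatment; no described analysis uses each symptom's own baseline rating, so it cannot by itself show greater improvement

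*Combined protocol and SAP*

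**What the plan says.** The Assessments section states that symptoms were rated at two time points: "The attending psychiatrists' assessments of eating disorder symptoms and psychopathology at baseline and at EOT were used". A baseline rating of each symptom should therefore be available alongside the EOT rating.

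The Statistics section uses these ratings in two separate ways:

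- For change over time, "the McNemar chi-square test was used to analyze the change in the incidence rates of symptoms". This is a paired analysis, and no split by weight group is described.
- For group contrasts, "for comparing groups of patients at EOT, Student's *t*-test and chi-square tests were used". Neither test carries a baseline term.

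The two-way repeated-measures analysis of variance is stated for BMI only.

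Under Results, the cohort is divided by BMI at EOT: "At EOT, a majority (73.1%) had achieved a normal body weight". The group at or above 18.5 is reported to have had a higher pre-treatment BMI, more weight gain over treatment, and "significantly lower rates of dietary restrictions, and less cognitive or behavioral symptoms of the eating disorder overall". No symptom rates are given for either group at either time point.

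**The concern.** Two questions can be asked of the two weight groups. One is whether they differed in symptoms at EOT. The other is whether symptoms resolved more often in patients who reached BMI 18.5. The described group comparison answers the first. Neither it nor the McNemar test, as described, answers the second, because no symptom analysis combines weight group with the patient's own baseline rating of that symptom.

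The gap matters because the groups are formed by an outcome, not by randomisation, and the document itself reports that they already differed in pre-treatment BMI. They may also have differed in symptoms at entry. If a symptom was less common at entry among those who later reached BMI 18.5, a lower EOT rate could simply carry that difference forward. The symptom result also stands in the same sentence as weight gain over treatment, so it is easily taken as a finding about improvement.

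**Working it through.** **Group sizes.** Participants gives "52 female patients diagnosed with AN" and Results gives 73.1% at BMI ≥ 18.5. 38/52 = 73.08%, which rounds to the stated figure (37/52 = 71.2% and 39/52 = 75.0% do not). The groups are 38 and 52 − 38 = 14.

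**What cannot be computed.** The documents give no symptom rates by group, so neither the baseline imbalance nor an adjusted result can be obtained. Everything below rests on assumed rates.

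**Simple illustration.** Suppose half of those with a symptom at entry still have it at EOT in both groups, and no one develops it newly. Suppose it was present at entry in 60% of the later BMI ≥ 18.5 group and 95% of the other.

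- EOT rates: 0.60 × 0.5 = 30.0% and 0.95 × 0.5 = 47.5%, a gap of 17.5 points with identical response. With equal baseline rates the gap is 0.
- At 38 versus 14 the pooled rate is (38 × 0.300 + 14 × 0.475)/52 = 0.347. Then z = 0.175/√(0.347 × 0.653 × (1/38 + 1/14)) = 1.18, two-sided p = 0.24. By exact enumeration, the chi-square would be significant in about 23% of such samples.

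**Range of assumptions.** Let a be the chance that a symptom present at entry persists and b the chance that it newly appears, both the same in the two groups, so there is no group difference given baseline. For baseline rate π, the EOT rate is πa + (1 − π)b. With b = 5%, exact binomial enumeration of the uncorrected Pearson chi-square (38 versus 14, two-sided 0.05) gives these proportions of significant results:

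| Baseline rate, BMI ≥ 18.5 vs < 18.5 | a = 50% | a = 60% | a = 80% |
|---|---|---|---|
| 80% vs 80% | 5% | 5% | 5% |
| 70% vs 90% | 9% | 11% | 16% |
| 60% vs 95% | 19% | 24% | 41% |
| 50% vs 95% | 29% | 37% | 61% |
| 85% vs 95% | 6% | 6% | 7% |
| 90% vs 95% | 5% | 5% | 5% |
| 90% vs 100% | 6% | 6% | 7% |
| 95% vs 100% | 5% | 5% | 5% |

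**Effect of using the baseline.** A Mantel-Haenszel test stratified by the symptom's baseline status was simulated 20,000 times for each of the first four rows, at a = 60% and 80%. It was significant in 4.6–4.9% of samples throughout. The excess in the table therefore comes from leaving out the baseline rating, and using it removes the excess.

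**The case against.** Five points can fairly be made against this.

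- **The text claims no differential improvement.** It says the groups differed at EOT, and a chi-square is a valid test of that. This stands. A reader might infer that symptoms resolved more often in patients who reached BMI 18.5, or because they reached it, but the document says neither.
- **A baseline symptom comparison may have been made.** The phrase "for comparing groups of patients at EOT" can mean groups formed at EOT. Pre-treatment BMI was compared between these groups, and Statistics mentions descriptive analysis of all variables. This stands too: a reader might infer that baseline symptoms were ignored altogether, but the text shows only that no such group comparison is described.
- **The size is assumed, and modest imbalance does little.** All patients met criteria for anorexia nervosa and had been ill for a mean of 13.29 months, so core symptoms may have been nearly universal at entry. The only symptom named specifically, dietary restriction, may be one of them. Rejection is then about 5–7%. Even the 30.0% versus 47.5% example would usually not reach significance. This limits the concern to symptoms that were not universal at entry; it does not remove it, because the baseline rates are not shown.
- **Adjustment cannot make the contrast causal.** Weight group is itself an EOT outcome, and one group has 14 patients. This stands, and it is a reason to present any adjusted result as descriptive and to supplement the EOT comparison, not replace it.
- **The main results are untouched.** Neither the 73.1% at normal weight nor the 42.3% needing no further treatment depends on this comparison. That is correct.

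**Conclusion.** The concern holds in a limited form. Baseline ratings were collected, and no described comparison of the weight groups uses them for symptoms. The reported lower rates in the BMI ≥ 18.5 group are therefore evidence about status at EOT and not, by themselves, about improvement.

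How much this matters depends on baseline rates that the documents do not give. Under identical persistence (50–80%) and 5% new onset, an EOT-only chi-square would be significant in about 9–61% of samples for baseline imbalances of 20–45 points, about 5–7% for symptoms nearly universal at entry, and 5% when baselines are equal.

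A reader might go further and conclude that the reported difference is an artefact of baseline imbalance. The documents do not support that: they do not show that baseline symptom rates differed between the groups at all.

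**What to change.** Keep the EOT comparison, labelled as a description of status at EOT, and make three additions.

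1. Report each symptom's baseline rate by weight group, next to its EOT rate.
2. For each symptom, compare EOT presence between weight groups with adjustment for, or stratification by, the patient's own baseline status on that symptom. Firth logistic regression or a Mantel-Haenszel test suits groups of 38 and 14. Where nearly everyone had the symptom at entry, compare resolution among those who had it.
3. State that this comparison is descriptive, because weight group is itself an EOT outcome and the smaller group has 14 patients. Word the conclusion as an association at EOT unless the adjusted result supports more.

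The cost is a few lines in Statistics, an extra column in the symptom table and a re-run on ratings already collected. Intervals will be wider. If baseline rates prove similar, the reported finding is strengthened.
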